**Table 2. Patient Participant Measures**

Construct	Measure	Assessment Time			
		Baseline (via paper survey)	3 months (via phone)	6 months (via phone)	9 months (Control Only; via phone)
Reason antidepressant was prescribed		X	X	X	X
Depression Symptoms and Severity	Personal Health Questionnaire Depression Scale (PHQ-8)	X	X	X	X
Anxiety Symptoms and Severity	Generalized Anxiety Disorder 7-Item Scale (GAD-7)	X	X	X	X
Functional Health Status	12-Item Short Form Survey (SF-12)	X	X	X	X
PGx Knowledge	Investigator Developed	X			X
Missed days of work	Work Productivity and Activity Impairment Questionnaire (WPAI)	X	X	X	X
Demographic information		X			
Health history	Smoking history, BMI	X			
Healthcare utilization	Physician visits, hospital and ER admissions	X	X	X	X
Adverse Drug Reactions	Antidepressant Side- Effect Checklist (ASEC)	X	X	X	X
Medication and medication changes	Medications prescribed and number of medication changes	X	X	X	X
Medication Adherence	Adherence to Refills and Medication Scale (ARMS)	X	X	X	X
	Pill count	X	X	X	X
	Three-Item Self-rated Adherence Scale	X	X	X	X

## 5.6 Data Analyses

In this study, we expect to enroll up to 30 physician participants and expect a retention rate of 90-100%. We also expect to enroll about 100 patient participants and expect a retention rate of 80% at the completion of this study.

Data from this study will be analyzed by the study statistician. Survey data will be analyzed using descriptive statistics. Multiple-choice questions will be analyzed using standard quantitative techniques including Chi square and t-test. Open-ended responses will be independently coded using qualitative methods, including any transcripts that result from the recorded survey responses.

Independent sample t-tests will be used to compare outcomes between intervention and control groups at each time point, as well as at similar time points after test results were released to physicians (i.e. baseline for intervention vs. 3 month for control group). Linear mixed models will assess the change in outcomes, as well as whether the change is similar between groups. This will be done by including time, study group, and a time by study group interaction as predictors of each outcome. Time will be considered in two ways, first as the time in study, and secondly as time since test results were released to physicians. In the latter, only data from 3-month to 9-month will be included for the control group, and baseline to 6-month for intervention group, due to timing of test result release. Models will be adjusted for patient demographics.

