## 3.0 Objectives

PGx testing could greatly improve the use of antidepressants by aiding prescribers in identifying proper medications for individual patients; thus potentially improving medication adherence, as well as reducing symptoms and antidepressant side effects.

This pilot study will explore the use of PGx testing in primary care, and is guided by several specific aims:

Specific Aim 1: To determine the effect of PGx testing on the primary outcome of physician treatment decisions, as measured by the change in the proportion of patients who are prescribed medications at baseline that are contraindicated according to the PGx test, compared to the proportion at six-month follow-up.

Specific Aim 2: To determine the effect of PGx testing on secondary outcomes measures of interest, including change in symptoms and severity and medication adherence from baseline to six-month follow-up.

Specific Aim 3: To determine the acceptability of PGx testing in primary care among patients and physicians.

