Patient participants will meet with study staff for consent and baseline data collection at a Michigan Clinical Research Unit (MCRU) in either Domino's Farms or the Cardiovascular Center. Once consent and baseline data collection are complete, participants will have their blood drawn by MCRU laboratory staff. A single 4 mL Lavender top EDTA tube of blood will be drawn. Once the blood draw is complete, study staff will send the sample to Progenity for analysis. After the baseline assessment is complete, patient participants will be randomized equally to either have their test results sent immediately to their participating primary care physicians once available, or to have their test results sent in three months. Randomization will be stratified by physician in ten block units to ensure balance by physician. PharmDs on the research team ([name] and [name]) will be available to consult with physician participants at any time during the study; however, our study PharmDs will meet with each participating physician at least once, when their first patient PGx test results are available to provide general, as well as patient specific education about the PGx test and results. These consultations will help physicians to interpret PGx test results, and may help to guide treatment decisions, if necessary. Study pharmacists or staff will not

provide PGx results to patients; it is up to the patient's physician to provide this information if he/she feels it is appropriate. Likewise, although study pharmacists may make treatment recommendations based on the PGx test results, it is up to the treating physician to decide whether to act on those recommendations. All intervention patient participants will be followed for a total of 6 months, with phone-based follow-up assessments occurring at 3- and 6-months. All control patients will be followed for 9 months, with phone-based follow-up assessments occurring at 3-, 6-, and 9-months. Please see Figure 2 for patient participant study flow.

Figure 1. Physician Participant Study Flow

[figure not shown]
[figure not shown]

Figure 2: Patient Participant Study Flow

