Physicians and patients enrolled in this study will be exposed to minimal risk. Participants in both arms of the study will undergo PGx testing. Physicians for intervention group participants will receive PGx test results as soon as they are available, whereas those participants in the waitlisted control group will receive their test results three months after enrollment. Because the current standard of care does not involve the use of PGx testing, our waitlisted control group is not exposed to any additional risk above and beyond usual care. To clarify, the intervention under investigation in this study is the PGx test. We will not directly intervene in the clinical care of a patient, as all clinical decision making is at the discretion of the physician managing a patient's care. All participants in this study may benefit because their antidepressant medication may be tailored to their pharmacogenomic profile. Although both populations of participants run risks associated with breaches of privacy due to electronic storage of study data, every effort will be made to minimize these risks.

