### **5.5.2 Patient Participants**

Patient participants will be screened for inclusion/exclusion criteria prior to consent and enrollment. After enrollment, all patient participants will complete a baseline, 3-, and 6-month assessment. Control patients will have an additional 9-month assessment of the previously mentioned items. All baseline data will be collected via paper forms and then transferred into REDCap, whereas 3-, 6-, and 9-month assessments will be conducted via phone and entered directly into REDCap by study personnel. The constructs, measures, and data collection times are shown in Table 2. In addition to these measures collected during data collection visits, data will be extracted from MiChart to document treatment, including medication changes, and healthcare utilization for patient participants during the study. We will also extract any available PHQ-9 and GAD-7 data, which is now collected as a part of routine clinical practice. Surveys/interviews will be audio recorded when permitted by participants.

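### Section 5.6 leaves baseline contraindicated status out as a covariate for Aim 1; a baseline-adjusted risk difference would usually be more precise, by an amount that depends on rates the documents do not give

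*Combined protocol and SAP*

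**What the plan says.** Specific Aim 1 (section 3.0) takes as its primary outcome "the change in the proportion of patients who are prescribed medications at baseline that are contraindicated" by the PGx test, compared with the proportion at six months. For each patient and visit this is a yes/no variable.

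Section 5.6 gives no method specific to that outcome. Its general methods are:

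- Unadjusted group comparisons: "Independent sample t-tests will be used to compare outcomes between intervention and control groups at each time point".
- A model of change: "Linear mixed models will assess the change in outcomes, as well as whether the change is similar between groups". The predictors are time, group and their interaction, with demographics as covariates. The baseline value is one of the responses, not a covariate.

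The section does not say which of the two is the main Aim 1 analysis.

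The data for adjustment are already collected. On genotype, section 5.1 says "Once consent and baseline data collection are complete, participants will have their blood drawn by MCRU laboratory staff", with randomisation afterwards, and "Participants in both arms of the study will undergo PGx testing". On drugs, Table 2 lists "Medications prescribed and number of medication changes" from baseline onward, and section 5.5.2 adds that "data will be extracted from MiChart to document treatment, including medication changes". Baseline contraindicated status can therefore be derived in both arms, unaffected by allocation, once the term has a written definition.

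**The concern.** A patient on a contraindicated drug at baseline is likely to be a main source of month-6 contraindicated prescriptions, so baseline status is a natural covariate. A follow-up-only t-test discards it. A difference in changes subtracts it in full, which over-corrects when many patients switch drug anyway. Regression adjustment estimates how much to subtract.

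Under randomisation, the month-6 difference, the difference in changes and the linearly adjusted difference all target the same between-arm risk difference (the adjusted one with a small-sample bias noted below). Adjustment therefore keeps Aim 1's focus on change. What is at stake is the width of the interval around the pilot's main product, an estimate of preliminary effectiveness from about 80 completers. Which planned analysis is the more precise depends on how long contraindicated prescriptions persist, and the documents do not say.

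**Working it through.** **Inputs from the documents.** Section 5.6 expects about 100 patients and 80% retention: 100 × 0.8 = 80, or 40 per arm under equal allocation. The plan states no power, effect size or contraindication rate, so it has no figure to reproduce. The roughly 10% CYP2D6 figure in section 2.0 is a metaboliser frequency, not a rate of contraindicated prescribing.

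**Assumed inputs, with ranges.** Share contraindicated at baseline p: 10, 20, 30, 40%. Controls still contraindicated at follow-up s_C: 50 to 90%. Intervention s_I: 10 to 80%, no higher than controls. Newly contraindicated q: 3 or 10%. This gives 168 scenarios.

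**What the mixed model estimates.** With complete data, and time fitted as visits (or as linear months 0, 3, 6 with the controls' month-9 visit left out), the time-by-group effect to month 6 equals the difference in mean changes. In 12 simulated complete trials without month 9 the largest gap was 1.4e-15. With month 9 included and time linear the two can differ.

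**Large-sample variances at n per arm.** Let m = p·s + (1−p)·q in each arm, V = p(1−p), S = the sum over arms of m(1−m), and C = V·[(s_C − q) + (s_I − q)].

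- t-test: S/n
- change: (S + 2V − 2C)/n
- baseline-adjusted: (S − C²/(2V))/n

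**Example A:** p = 30%, controls keep 90%, intervention keeps 40%, q = 3%.
- m = 0.291 and 0.141; V = 0.21; S = 0.2063 + 0.1211 = 0.3274; C = 0.21 × (0.87 + 0.37) = 0.2604.
- Numerators: t-test 0.3274; change 0.3274 + 0.42 − 0.5208 = 0.2266; adjusted 0.3274 − 0.0678/0.42 = 0.1660.
- Variance cut: 1 − 0.1660/0.2266 = 27% against change, 49% against the t-test.

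**Example B:** as A, but controls keep 55%, plausible at month 6 after release.
- S = 0.2725; C = 0.21 × (0.52 + 0.37) = 0.1869.
- Numerators: t-test 0.2725; change 0.3187; adjusted 0.1894.
- Cut: 31% against the t-test, 41% against change. The better planned analysis has switched from change to the t-test.

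**Simulated 95% half-widths (points) and power at 40 per arm, p = 30%, intervention keeps 40%; adjusted interval by HC3:**

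| Controls keep | New | Half-width: t-test / change / adjusted | Power: t-test / change / adjusted |
|---|---|---|---|
| 90% | 3% | 18.0 / 14.9 / 13.2 | 38 / 52 / 60% |
| 90% | 10% | 19.3 / 18.1 / 16.2 | 33 / 36 / 43% |
| 55% | 3% | 16.3 / 17.7 / 14.0 | 9 / 8 / 9% |
| 55% | 10% | 18.1 / 20.7 / 16.9 | 8 / 7 / 8% |

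At p = 10%, 90% against 40% kept and 3% new, power is 13 / 13 / 12%: no gain.

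**Whole grid at 40 per arm.** The t-test had the smaller variance in about 100 scenarios and change in about 68. The adjusted estimate beat both in all 168: a cut of about 2-36%, median about 19%, against the better, and a median of about 40% against the worse. Its HC3 interval was narrower than both planned intervals in 163 of 168.

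**Where adjustment does worse.**
- Weak persistence, below the grid (controls keep 20%, intervention 10%, 10% new): adjusted variance about 1.007 times the t-test's. With no baseline/follow-up association: 1.013-1.015 times.
- p = 10%, 90% against 40% kept: true difference 0.10 × (0.4 − 0.9) = −5.0 points, mean adjusted estimate −4.5, a shrinkage of 0.5/5.0 = 10%. Mean squared error over the grid still falls by at least 2.6%.
- Coverage of the adjusted interval is 92-98% over the grid, but 76% at a 5% baseline share with event rates of 5% against 1%, where the t-interval covers 87%.

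**Continuous outcomes.** With equal variances and baseline/follow-up correlation ρ, the cut is ρ² against the t-test and (1−ρ)/2 against change. At assumed ρ of 0.3, 0.5, 0.7 that is 9, 25, 49% and 35, 25, 15%.

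**The case against.** The strongest reply is that the plan does use baseline: it is a time point in the mixed model, and Aim 1 is itself a change. Both planned analyses are unbiased for the risk difference, and the t-interval covers about 95% unless rates are near zero. This is also a pilot with no power claim. All of that stands. A reader might infer that section 5.6 ignores baseline altogether or yields an invalid test; the documents support neither.

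The second reply concerns timing. Because the "waitlisted control group will receive their test results three months after enrollment", controls have had results for about three months at the six-month comparison. Their prescriptions may then depend little on baseline, and the gain may be small or slightly negative. This also stands. A reader might infer that adjustment costs nothing and always wins because it won in every grid scenario. But the grid stops at controls keeping 50%, its median weights arbitrary scenarios equally, and the shrinkage and sparse-data coverage are real costs. The documents give no rates that would rule out the unfavourable cases. When persistence is low, though, change suffers most: at 30% against 20% kept, its variance was 1.83 to 2.29 times the t-test's, while the adjusted estimate's was 0.91 to 0.95 times.

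A third point is that logistic adjustment would not deliver the gain. The standard error of the log odds ratio rose in simulation (0.63 to 0.91 at a 20% baseline share, 90% against 40% kept), because the conditional odds ratio is a different, larger quantity. Hence the restriction to the risk-difference scale.

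**Conclusion.** The point holds as one of efficiency, not validity. Baseline contraindicated status is a covariate in neither planned analysis, and adjusting for it would usually tighten the Aim 1 estimate: about 2-36% less variance (median about 19%) than the better planned analysis and a median of about 40% less than the worse, at 40 per arm. Every rate behind these figures is assumed.

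The gain shows in interval width more than in power, which barely moves at a 10% baseline share or once controls' results are out. A reader might infer from the variance figures that adjustment rescues the six-month comparison. It does not: the month-3 release narrows the contrast between arms whatever estimator is used.

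**What to change.** 1. Name one main Aim 1 estimate: the month-6 between-arm risk difference adjusted for baseline contraindicated status, by linear regression with an HC3 95% interval, or a standardised estimate. Do not use an odds ratio.
2. Replace the unadjusted follow-up t-tests for PHQ-8, GAD-7 and adherence with models adjusted for the baseline value.
3. Fix in advance a numeric sparse-data trigger, based on the number contraindicated at baseline, and a fallback such as the stratified Newcombe interval. The tested points were about 4 per arm (0.10 × 40; coverage 92-98%) and about 2 per arm (0.05 × 40, with the rare event rates above; 76%), so the threshold should be confirmed by simulation in that region. Keep the fallback for sparse data: it covered 96-100% but was narrower than the t-interval in only 45% of scenarios.
4. State the downsides: slight variance loss if baseline barely predicts month 6, and about 10% shrinkage at a 10% share.
5. Plan for missing visits. With 20% lost at month 6 at random, complete-case adjusted regression was level with or up to 3% worse than the planned mixed model in 3 of 32 scenarios. A mixed model of the 3- and 6-month values with arm-by-visit and baseline-by-visit terms had the smallest variance in all 32, but its interval coverage was not tested and should be checked before adoption.

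The cost is analysis-plan wording and no new data. It needs one written rule for what counts as contraindicated, applied identically at baseline and follow-up (including drugs read from MiChart), and a rule for patients without a usable test result.

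### Section 5.6 gives the yes/no primary outcome and the counts only t-tests and linear mixed models; with an unstated covariance structure, the test of change can run at about 6.5–12% instead of 5%

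*Combined protocol and SAP*

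**What the plan says.** Specific Aim 1 (section 3.0) names the primary outcome as the "change in the proportion of patients who are prescribed medications at baseline that are contraindicated according to the PGx test", set against the proportion at six months. For each patient that is yes or no at each visit.

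Table 2 also lists "Medications prescribed and number of medication changes" and "Physician visits, hospital and ER admissions", which are counts.

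Section 5.6 gives two tools for comparing the arms. The first is a t-test: "Independent sample t-tests will be used to compare outcomes between intervention and control groups at each time point". The second is a model for change: "Linear mixed models will assess the change in outcomes, as well as whether the change is similar between groups", fitted by "including time, study group, and a time by study group interaction as predictors of each outcome". Time is taken first from study entry and then from release of the test results.

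Chi-square appears once, for survey items: "Multiple-choice questions will be analyzed using standard quantitative techniques including Chi square and t-test". The section names no logistic, GEE, Poisson or negative binomial model, no random-effects or covariance structure, and no robust standard error.

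**The concern.** A linear mixed model with one residual variance assumes that an outcome varies equally at every visit. A proportion does not: its variance is p(1−p), so it shrinks as p falls. If PGx results change prescribing, p should fall after release. Pooling one variance over a high-rate visit and two low-rate visits then understates the variance of the baseline-to-follow-up change, which is the quantity Aim 1 asks about.

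The t-interval has a related weakness. When an arm has few events or none, its estimated variance is close to zero, and the interval for the difference can be too short.

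At stake are the type I error of the model tied to the primary outcome, and the interval that a pilot of preliminary effectiveness would report.

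**Working it through.** **Inputs from the documents.** Section 5.6: "We also expect to enroll about 100 patient participants and expect a retention rate of 80% at the completion of this study". Section 5.1 randomizes equally, so 100/2 = 50 per arm enrolled and 0.80 × 50 = 40 per arm at completion. Visits at baseline, 3 and 6 months (Table 2), plus 9 months for controls.

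**Assumptions.** The documents give no rate of contraindicated prescribing, alpha, power or covariance structure, so there is no stated figure to reproduce. I take two-sided alpha 0.05 and a range of rates. The introduction's figure of about 10% is a CYP2D6 metabolizer frequency, not this rate.

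**1. Single-visit t-test, equal true rates.** Exact type I error, summed over all pairs of binomial counts:

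| Rate | 40 per arm | 50 per arm |
|---|---|---|
| 2% | 0.7% | 1.3% |
| 5% | 4.3% | 4.3% |
| 10% | 5.9% | 4.8% |
| 20% | 5.1% | 4.9% |

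Uncorrected chi-square gives 4.3% and 5.9% at rates of 5% and 10% with 40 per arm, the same as the t-test. For counts (means 0.05 to 2, Poisson or overdispersed) the t-test's size is 2.8–5.5%. The single-visit test holds its level.

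**2. t-interval for the difference, unequal true rates.** Interval: d ± t × √[(a(1−a) + b(1−b))/(n−1)], where a and b are the observed proportions. Exact coverage of the nominal 95% interval:

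| True rates | 40 per arm | 50 per arm | Misses at 40 per arm: benefit understated / overstated |
|---|---|---|---|
| 2% vs 10% | 91.1% | 93.5% | 8.2% / 0.75% |
| 1% vs 9% | 88.0% | 92.9% | 11.4% / 0.6% |
| 2% vs 5% | 86.5% | 91.5% | 12.9% / 0.6% |

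At 10% vs 30% with 40 per arm, coverage is 94.9%. Newcombe's interval covers 98–99% in the low-rate cases.

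**3. Linear mixed model, change from first to last of three visits.** In a balanced random-intercept model, the model's variance of a within-patient change is the average, over the three pairs of visits, of the variance of the difference. Compare it with the true variance of the first-to-last change. The approximate type I error is 2 × P(Z > 1.96/√ratio).

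*Visits independent, 10% → 2% → 2% in both arms.* The visit variances are 0.09, 0.0196 and 0.0196. True: 0.09 + 0.0196 = 0.1096. Model: 2 × (0.09 + 0.0196 + 0.0196)/3 = 0.0861. Ratio 1.27; 1.96/√1.27 = 1.74; type I error about 8.2%.

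*Status never reverts, same rates.* A change has probability 0.08, so its variance is 0.08 × 0.92 = 0.0736. The three pairs give 0.0736, 0.0736 and 0. Model: their mean, 0.0491. Ratio 1.5; 1.96/√1.5 = 1.60; type I error about 11%.

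Simulation (40,000 runs per setting, 40 and 50 per arm) agrees:

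| Rates in both arms | Independent | Moderate correlation | Never reverts |
|---|---|---|---|
| 10% → 5% → 5% | 6.5–6.6% | 6.5–6.6% | 11.1–11.8% |
| 10% → 2% → 2% | 8.6–8.9% | 8.6–8.7% | 12.2–12.3% |
| 20% → 10% → 5% | 5.8% | 6.8–7.1% | 10.3–10.9% |

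Two controls isolate the cause. With constant rates, and independent or moderately correlated visits, the three-visit test stays at 5.1–5.4%. With two visits, where the test is a t-test on change scores, it stays at 4.4–6.3% under the same falling rates. The excess comes from pooling unequal variances over three visits, not from low rates alone.

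**4. Does the design produce this pattern?** Section 5.1 releases control results at three months. On the second time scale in section 5.6 both arms are aligned on release, so equal falls in both arms is the null hypothesis being tested. If few patients return to a drug once taken off it, the right-hand column is the nearest.

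**The case against.** The strongest defence is that the t-test is sound here, and for a single visit that stands. At the lowest rates it is conservative.

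A reader might infer that low rates make the t-test turn non-significant results into significant ones, and might point to a table such as 0/40 vs 4/40, where the t-test gives p = 0.041 and Fisher's test p = 0.116. That does not follow. Chi-square gives p = 0.040 and Barnard's exact test p = 0.043 on the same table, and the Miettinen-Nurminen interval (upper limit −0.7 points) also excludes zero. The gap reflects Fisher's conservatism: its size at 40 per arm is 0.4% and 1.7% at rates of 5% and 10%. Nor do the documents say that low rates are expected.

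The interval misses also fall mainly on the side that understates benefit, so they do not support a charge of overclaiming. And 40 per arm is the end-of-study figure; at month 3, or for drug status taken from MiChart, the number could be nearer 50, where under-coverage is milder.

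It is also fair that section 5.6 does not commit to a single-variance random-intercept model. An unstructured covariance or robust errors would remove most of the excess. But neither is stated, and the simple model is a natural reading of the text.

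For counts, one might fear the same inflation. The t-test keeps its size, and a plain Poisson model would be worse: at mean 1 with overdispersion k = 0.5 and 40 per arm, its size is 25.6% against 4.6% for the t-test. For counts the point is therefore a missing specification, not a demonstrated error.

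**Conclusion.** The point holds in limited form. Section 5.6 names no analysis suited to a yes/no primary outcome or to counts. Two consequences follow.

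The more important one is that the mixed-model test of change has type I error of about 6.5–12% instead of 5%. It is highest, about 10–12%, if status never reverts; one independent-visit pattern gave only 5.8%. This rests on three visits, a simple random intercept with one residual variance, and rates that fall equally in both arms.

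The lesser one is t-interval coverage of 86–91% (40 per arm) or about 91–93% (50 per arm) when rates are low and unequal.

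Every rate used is an assumption. A general claim that non-significant findings will read as significant is not supported. For a pilot the severity is moderate.

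**What to change.** In section 5.6:

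- **Aim 1 across visits:** use logistic GEE with small-sample robust standard errors, a mixed logistic model, or a linear model with robust errors, and report a marginal risk difference. If an arm has no events at a visit, the logistic fit may fail, so name a fallback in advance.
- **Aim 1 at each visit:** report the risk difference with a Newcombe or Miettinen-Nurminen interval, choosing one in advance since the two can disagree about zero. Fisher's test need not be required.
- **Visits, admissions and number of medication changes:** use negative binomial or robust-variance models, not plain Poisson.
- **Scale scores (PHQ-8, GAD-7, SF-12 and similar):** keep the t-tests and linear mixed models, and state the covariance structure.

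The cost is a few sentences and standard software, with no new data. Some intervals will be slightly wider, and a small-sample correction is needed if events are few.

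### The release-aligned analyses start the intervention clock at baseline, before the blood is drawn, and no stated order keeps the control 3-month call ahead of release

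*Combined protocol and SAP*

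**What the plan says.** Section 5.6 (Data Analyses) describes two sets of between-arm t-tests. One compares the arms at each study visit. The other compares them "as well as at similar time points after test results were released to physicians (i.e. baseline for intervention vs. 3 month for control group"). The linear mixed models likewise use two time scales: time in study, and "secondly as time since test results were released to physicians". For the second scale, "only data from 3-month to 9-month will be included for the control group, and baseline to 6-month for intervention group".

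Section 5.1 (Study Design) gives the order of events at entry: "Once consent and baseline data collection are complete, participants will have their blood drawn by MCRU laboratory staff". Next, "Once the blood draw is complete, study staff will send the sample to Progenity for analysis". Patients are randomised to "have their test results sent immediately to their participating primary care physicians once available, or to have their test results sent in three months". Later in the same section the release rule is repeated by arm: "Physicians for intervention group participants will receive PGx test results as soon as they are available". For the other arm the rule is a fixed date counted from entry: "those participants in the waitlisted control group will receive their test results three months after enrollment". Control phone assessments are set for 3, 6 and 9 months. Section 4.3 adds that the laboratory reports to study staff, who pass the result to the physician through MiChart.

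**The concern.** The release-aligned analyses are meant to put both arms on a common clock that starts when the physician receives the result. In the intervention arm the plan starts that clock at a visit held before any sample exists. Each later intervention visit then carries a label that is too large by the time from baseline to release.

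In the control arm, the release and the 3-month call are due at the same time. The readable text gives no call window and no rule on which comes first. This matters beyond the aligned analyses, because month 3 is the only follow-up assessment at which controls can still be unreleased. It is therefore the only follow-up contrast between a released and an unreleased arm.

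**Working it through.** The documents give no figure for elapsed time since release, so there is nothing to reproduce. The check sets the sections side by side and then does timeline arithmetic.

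**Order of events, intervention arm (sections 5.1 and 4.3).** Baseline data, blood draw, shipment, laboratory analysis, report to study staff, release through MiChart. Baseline comes first and release last, so the lag L from baseline to release is above zero for every intervention patient. Section 5.6 nevertheless gives intervention baseline as its example of a time point after release. This contradiction needs no assumption.

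**Order of events, control arm (section 5.1).** Release at three months after enrolment; call at 3 months. Let w be the call date minus the release date. The readable text does not determine the sign of w.

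**Inputs.**
- Nominal release-aligned visits: 0, 13 and 26 weeks, taking 3 months as 13 weeks. These are baseline, month 3 and month 6 for intervention, and months 3, 6 and 9 for control (section 5.6).
- L: not stated; assumed 1 to 4 weeks.
- w: not stated; assumed -2 to +2 weeks.

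**Formulas.** True time since release is nominal time minus L in the intervention arm, and nominal time plus w in the control arm. The between-arm misalignment is L + w.

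| Nominal week | Intervention, L = 1 to 4 | Control, w = 0 | Control, w = -2 to +2 |
|---|---|---|---|
| 0 | -1 to -4 | 0 | -2 to +2 |
| 13 | 12 to 9 | 13 | 11 to 15 |
| 26 | 25 to 22 | 26 | 24 to 28 |

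**Size when the control call coincides with release (w = 0).** The misalignment is L alone. As a share of the 3-month interval:
- 1/13 = 7.7%
- 2/13 = 15.4%
- 3/13 = 23.1%
- 4/13 = 30.8%

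**Size across the assumed w.** The misalignment runs from 1 - 2 = -1 week (-7.7%) to 4 + 2 = +6 weeks (46.2%). It is zero when the control call precedes release by exactly L.

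**Effect on the mixed model.** Take a linear course of -1 unit per month from release, observed at nominal months 0, 3 and 6. With lags of 0, 0.25, 0.5 and 1 month, the fitted slope is -1 each time, and the intercept moves to 0, 0.25, 0.5 and 1. A lag common to all patients in an arm therefore leaves the linear slope, and so the time-by-group interaction, unchanged. The slope loses this protection if L or w varies between patients, if the course is not linear, or if some control month-3 values already reflect a released result. The aligned t-tests compare values at matched visits and so do not have this protection.

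**The case against.** The strongest defence is that intervention baseline and control month 3 are meant as each arm's last assessment before release. That is a sensible alignment, and on this reading the fault lies mainly in the wording. It works, however, only if control calls precede release, which the readable text does not say. It also leaves the later visits at different distances from release, unless the control call happens to precede release by the same lag.

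Second, the model may be intended to use actual release dates, with intervention baseline at a negative time. The windows in section 5.6 do not exclude this, but nothing there says so. The t-tests pair nominal visits in either case.

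Third, the slope argument above is correct and limits the harm. The 8% to 31% is a shortfall in weeks of exposure, not a bias in any estimate.

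Fourth, a control call a few days after release may carry little effect. The physician must first receive the result and choose to act on it, and section 2.0 puts the time from starting treatment to clinical effect at two to four weeks. Medication changes are also extracted from MiChart (section 5.5.2), and the primary outcome in section 3.0 runs from baseline to six months. All of this stands, and it keeps the control-arm point to a possibility of unknown size.

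Finally, Figure 2, the patient flow, is not shown and may give the order of call and release. Its absence is not counted against the plan.

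**Conclusion.** The point holds for the intervention arm without any assumption: section 5.6 treats as post-release a visit that section 5.1 places before the blood draw. Nominal time therefore overstates intervention exposure by the turnaround. With an assumed turnaround of 1 to 4 weeks and a control call on the release date, the aligned 3-month comparison is 9 to 12 weeks against 13, a shortfall of 8% to 31%. In the control arm the 3-month assessment is unprotected in the readable text, and the extent of any post-release data is unknown.

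A reader might infer three stronger things that the documents do not support:
- **That time since release is wrong in both arms.** If control calls fall on or just before release, the control zero is correct or is a proper pre-release measurement.
- **That about half of the control 3-month calls follow release.** This would require calls to be spread evenly around the release date, and no figure in the documents says so.
- **That the mixed-model slopes must be biased.** A constant lag leaves linear slopes unchanged; bias requires lags that vary, a non-linear response, or post-release control data.

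The defect does not invalidate the trial. It is more than missing detail, because a stated alignment rule conflicts with the stated procedures and is nearly free to correct.

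**What to change.** 1. Log the actual MiChart release date for every patient in both arms, and state in section 5.6 that time since release in the mixed model is computed from that date, so that assessments before release take negative values.
2. Reword section 5.6 so that intervention baseline and control month 3 are described as each arm's last assessment before release.
3. Schedule the control 3-month call to close on or before the planned three-month release date, leaving the release date unchanged. Flag any call made after release, and repeat the month-3 and release-aligned analyses without those calls as a sensitivity analysis.

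The cost is one logged date per patient, slightly tighter call scheduling in the control arm, and a few sentences in section 5.6. Study staff already release the results (section 4.3), so the date can be captured as they do so. No visits or patients are added.
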